6.3.4 At screening, annually and as clinically indicated

Ophthalmic exam (See Appendix G (section 11.7) for Ophthalmic Exam Worksheet). The exams will be performed one year after the day 1 cycle 8 visit +/- 2 months and every year thereafter until the patient is off treatment.

6.4 Continued Treatment after Disease Progression

See section 6.8, correlative study procedures for more information.

6.5 End of Treatment

This visit should occur in patients when they permanently stop treatment for any reason, and should be performed 30 days (+/-7 days) after the last dose of study medication.

Clinical evaluation: complete history, physical examination (to also include vital signs and weight), and ECOG performance status.

Laboratory studies:

- **Hematology**: Hematology includes the following parameters: CBC with differential, Hgb, and platelet count.
- **Serum Chemistries**: These include the following parameters: creatinine, sodium, potassium, calcium, magnesium, phosphorus, albumin, total bilirubin, AST (SGOT) and ALT (SGPT).

Concomitant medications: Review any additions or deletions

Patient Diary: Review Diary

Toxicity Assessment: Using NCI CTCAEv4; Patients who have an ongoing grade 4 or serious AE (SAE) at the time of discontinuation from treatment will continue to be followed until the event is resolved or deemed irreversible by the investigator, and will then be followed-up per protocol. Toxicity assessment should include interrogation of the patient related to any visual changes they may be experiencing.

Tissue acquisition: Biopsy of accessible tumor will be done in patients who stop treatment due to progression, if possible within 7 business days of documented disease progression, and optimally within 4 hours of taking that day's study medication. Post-treatment biopsies will not be required for patients removed for reasons other than disease progression. See section 6.7 and laboratory manual.

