4.4.12 Non-specified Toxicities Attributable to Drug Therapy

CTCAE Grade	Action and Dose Modification for Dabrafenib and Trametinib
1 or tolerable Grade 2	Continue study treatment at current dose level Monitor closely Provide supportive care according to institutional standards
1 st , 2 nd , or 3 rd occurrence of intolerable Grade 2 or any Grade 3	Interrupt study treatment Monitor closely Provide supportive care according to institutional standards When toxicity resolves to ≤grade 1, restart study treatment reduced by one dose level
4th occurrence of intolerable Grade 2 or any Grade 3	Discontinue treatment
4	Interrupt study treatment Monitor closely Provide supportive care according to institutional standards Restart with study treatment reduced by one dose level once toxicity resolves to ≤grade 1 If the grade 4 toxicity recurs, once resolves to ≤grade 1, restart at two dose levels lower than the starting dose or permanently discontinue study treatment at discretion of the investigator For 3 rd occurrence, discontinue treatment

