^{3a} Repeat ophthalmic exams annually while on treatment and if clinically-indicated due to the presence of ocular symptoms. The exams will be performed one year after the day 1 cycle 8 visit +/- 2 months and every year thereafter until the patient is off treatment. See Appendix G (section 11.7) for Ophthalmic Exam Worksheet.

⁴The end of treatment visit should only occur when patients permanently stop study treatment and should be performed 30 days (+/-7 days) after the last dose of study medication. All adverse events and concomitant medications should be followed up until the 30-day End of Treatment (EOT) visit. Patients who have an ongoing \geq grade 2 or serious AE (SAE) at the EOT will continue to be followed until the event is resolved or deemed irreversible by the investigator. See section 6.5 for follow-up schedule for patients who discontinue study treatment due to progression or for other reasons.

⁵Complete history at baseline only, thereafter focused history on symptoms/toxicity; physical exam to include height (baseline only), weight, and vital signs

⁶Dermatologic exams will continue every 3 months for the first 6 months following discontinuation from dabrafenib, and should include monitoring for cutaneous and non-cutaneous secondary/recurrent malignancies.

⁷Serum B-HCG within 48 hours prior to first dose of study medication for WOCBP; serum B-HCG will be repeated only if clinically appropriate.

⁸**Hematology:** CBC with differential, Hgb, and platelet count; **Serum chemistries:** creatinine, sodium, potassium, calcium, magnesium, phosphorus, LDH and albumin. **Liver function tests:** total bilirubin, AST (SGOT) and ALT (SGPT). Also see sections 4.4.9.3 and 11.4.4 for required monitoring in event of liver toxicities, including possibility of blood draw for pharmacokinetics. If screening evaluations of these tests are performed within 48 hours prior to Day 1 of treatment, they do not need to be repeated.

⁹Coagulation profile includes prothrombin time or INR, and activated partial thromboplastin time.

¹⁰Toxicity assessment should include interrogation of the patient related to any visual changes they may be experiencing. Patients who have an ongoing \geq grade 2 or serious AE (SAE) at the time of discontinuation from treatment will continue to be followed until the event is resolved or deemed irreversible by the investigator.

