6.6 Follow-up Assessments

Patients who come off therapy due to progression will enter the follow-up phase every 3 months for up to 1 year from study entry to document survival (no tumor measurement per study protocol will be necessary after progression). Patients who come off therapy for reasons other than progression will enter the follow-up phase every 3 months for up to 1 year from study entry to document survival. If tumor assessments are available for patients who have not yet experienced progressive disease (PD), enter the follow-up tumor evaluations in the eCRF until PD is confirmed. Regardless, of the reason that a patient comes off treatment, dermatologic exams will continue every 3 months for the first 6 months following discontinuation from dabrafenib, and may be done by a physician local to the patient. Only after these dermatologic exams are complete is the patient considered off follow-up, even if they do not require survival follow-up for this entire 6 month period.

Patients who have an ongoing \geq Grade 2 AE or SAE at the time of discontinuation from treatment will continue to be followed in clinic until the event is resolved or deemed irreversible by the investigator.

For subjects who are withdrawn from study treatment, but are later placed back on the trametinib/dabrafenib combination therapy, a biopsy may be collected from the former study subject at the time of progression from the standard of care trametinib/dabrafenib therapy. These subjects will then remain on study for safety monitoring, in relation to the biopsy procedure, for 30 days. Subjects who have an ongoing \geq grade 2 or serious AE (SAE) related to the study procedure at 30 days will continue to be followed until the event is resolved or deemed irreversible by the investigator.

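### Section 6.5 sets continued adverse-event follow-up at grade 4 or serious, while sections 6.1 and 6.6 set it at grade 2 or higher or serious

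*Combined protocol and SAP*

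**What the plan says.** Four places in the current protocol text say which unresolved adverse events must be followed after treatment ends.

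- **Section 6.5, Toxicity Assessment:** follow-up continues for "Patients who have an ongoing grade 4 or serious AE (SAE) at the time of discontinuation from treatment".
- **Section 6.6:** "Grade 2 AE or SAE at the time of discontinuation from treatment will continue to be followed in clinic". A ≥ sign stands immediately before the quoted words.
- **Section 6.1, footnote 10:** "grade 2 or serious AE (SAE) at the time of discontinuation from treatment will continue to be followed until the event is resolved", again with ≥ immediately before.
- **Section 6.1, footnote 4:** "grade 2 or serious AE (SAE) at the EOT will continue to be followed until the event is resolved or deemed irreversible by the investigator", again with ≥ immediately before.

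Footnote 4 goes on: "See section 6.5 for follow-up schedule for patients who discontinue study treatment due to progression or for other reasons". Section 6.5 describes the End of Treatment visit. The three-monthly follow-up schedule, for patients who stop because of progression and for those who stop for other reasons, is in section 6.6.

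**The concern.** All four statements serve one purpose: they say when an unresolved toxicity must still be followed after treatment has stopped. One of them sets the bar two grades higher than the others, and no clause says which text prevails.

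The odd one out is in the section staff would open to run the End of Treatment visit. Footnote 4 makes this worse, because it states the lower threshold and then directs the reader to the section with the higher one.

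What is at stake is the follow-up of non-serious grade 2 and grade 3 toxicities. Under section 7.2, routine documentation of non-serious events ends with the 30-day period after treatment stops. The continued-follow-up rule is what carries an unresolved event past that point. If a site takes its threshold from 6.5, patients with persisting moderate or severe toxicity may not be followed to resolution, and the record of how these events end will be incomplete.

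**Working it through.** No arithmetic applies. The check sets the four statements side by side and then asks which events fall between the two thresholds.

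| Place | Threshold | Judged at | Followed until |
|---|---|---|---|
| 6.5 | grade 4 or serious | discontinuation | resolved or judged irreversible |
| 6.1 footnote 10 | ≥ grade 2 or serious | discontinuation | same |
| 6.6 | ≥ grade 2 or serious | discontinuation | same |
| 6.1 footnote 4 | ≥ grade 2 or serious | 30-day End of Treatment visit | same |

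1. **Same rule, different grade.** Section 6.5, footnote 10 and section 6.6 share the time point and the end point. Footnote 4 is judged at the visit that 6.5 describes. Nothing gives 6.5 a separate population or purpose.

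2. **Not a reading artefact.** A ≥ sign lost before grade 4 would not reconcile the texts, because the grade itself differs (4 against 2). Nor is any of the four statements superseded amendment-log wording.

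3. **Events in the gap.** Serious events are covered under either threshold, and so is grade 4. What remains is a non-serious grade 2 or grade 3 event that is still present when treatment stops.

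4. **Whether such events can end treatment.** They can.
   - In the rash table (section 4.4.1.1), a rash of grade 3 or higher that has not come down to grade 2 within 4 weeks leads to permanent discontinuation. A non-serious grade 3 rash handled this way is by definition ongoing at discontinuation, and the table gives no rule for following it to resolution.
   - In section 4.4.12, treatment is discontinued at the "4th occurrence of intolerable Grade 2 or any Grade 3", and that table has no follow-up rule either.

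5. **Events protected by other rules.**
   - Section 7.1.4 defines several events as serious, including retinal pigment epithelial detachment, retinal vein occlusion, new malignancies and specified falls in ejection fraction.
   - Sections 4.4.3.3, 4.4.4 and 4.4.9.2 set their own monitoring for ejection fraction, retinal and liver events.
   - Section 4.4.5 requires abnormal lung function tests in grade 2 and 3 pneumonitis to be repeated until normal.
   - Section 6.6 keeps dermatologic exams going for 6 months after dabrafenib stops.

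6. **Size.** One of four statements differs. Appendix H cannot supply a count of affected events: it reports maximum grade in another trial, not events ongoing at discontinuation.

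**The case against.** The strongest reply is that the broader rule already binds. Section 6.5 does not restrict follow-up to grade 4 or serious events, so the four statements can be read cumulatively, and a site that follows everything from grade 2 upward complies with all of them. Section 6.5 is a visit checklist, whereas 6.6 is the section that governs follow-up. The toxicity row of the schedule table carries footnotes 4 and 10, both of which state the lower threshold. Sections 4.4 and 4.8 also say that patients taken off therapy are to be followed according to the protocol. Harm therefore requires a site to read 6.5 in isolation. The wrong pointer in footnote 4 looks like section-number drift, since section 6.4 likewise cites 6.8 for correlative procedures that are in 6.7.

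The 4.4.12 example can also be challenged. The first three occurrences each call for a one-level reduction, but section 4.4 provides two reduced levels and stops therapy if more than two reductions are needed. Treatment might therefore end before the fourth-occurrence row is reached.

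Much of this stands as a limit on the harm. The compatible reading is real, and a careful site would do the right thing. It does not make the 6.5 threshold correct: if grade 2 or higher is intended, the grade 4 wording adds nothing and can only mislead. The clauses in 4.4 and 4.8 set no grade, so they return the reader to the conflicting sections. The dose-reduction cap changes when treatment stops under 4.4.12. It does not change the fact that it stops for a non-serious grade 2 or 3 event, and the rash example does not depend on it. Dermatologic exams would bring a patient with rash back to a physician, but they are scheduled examinations, not a duty to follow the event to resolution.

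**Conclusion.** The concern holds. Section 6.5 is inconsistent with footnotes 4 and 10 of section 6.1 and with section 6.6 on an operative safety rule, and footnote 4 points to the wrong section for the follow-up schedule.

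The severity is minor. The exposure is limited to non-serious grade 2 and 3 toxicities that are ongoing when treatment stops and have no follow-up rule of their own, and it arises only at a site that takes its threshold from 6.5. The frequency cannot be estimated from the documents. The primary kinome analysis, the response and survival endpoints, the sample size and the power are untouched.

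The conclusion assumes that the threshold shared by three of the four statements is the intended one. If the sponsor in fact meant grade 4, the conflict would remain, and the other three places would need to change instead.

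**What to change.** Make two edits:

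- In section 6.5, Toxicity Assessment, replace *grade 4* with *≥ grade 2*, so that the sentence matches footnotes 4 and 10 and section 6.6.
- In footnote 4 of section 6.1, change the cross-reference for the follow-up schedule from 6.5 to 6.6.

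The cost is one phrase and one section number, which can go into the next amendment. No visit, test or data item is added beyond what sections 6.1 and 6.6 already require.

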6.6 Follow-up Assessments

Patients who come off therapy due to progression will enter the follow-up phase every 3 months for up to 1 year from study entry to document survival (no tumor measurement per study protocol will be necessary after progression). Patients who come off therapy for reasons other than progression will enter the follow-up phase every 3 months for up to 1 year from study entry to document survival. If tumor assessments are available for patients who have not yet experienced progressive disease (PD), enter the follow-up tumor evaluations in the eCRF until PD is confirmed. Regardless, of the reason that a patient comes off treatment, dermatologic exams will continue every 3 months for the first 6 months following discontinuation from dabrafenib, and may be done by a physician local to the patient. Only after these dermatologic exams are complete is the patient considered off follow-up, even if they do not require survival follow-up for this entire 6 month period.

Patients who have an ongoing \geq Grade 2 AE or SAE at the time of discontinuation from treatment will continue to be followed in clinic until the event is resolved or deemed irreversible by the investigator.

For subjects who are withdrawn from study treatment, but are later placed back on the trametinib/dabrafenib combination therapy, a biopsy may be collected from the former study subject at the time of progression from the standard of care trametinib/dabrafenib therapy. These subjects will then remain on study for safety monitoring, in relation to the biopsy procedure, for 30 days. Subjects who have an ongoing \geq grade 2 or serious AE (SAE) related to the study procedure at 30 days will continue to be followed until the event is resolved or deemed irreversible by the investigator.

6.7 Correlative Study Procedures

For both those patients who do and do not co-enroll into LCCC1108, we will ask for a blood sample (~8mLs in a yellow-top ACD tube) to ensure sufficient germline DNA in the event tissue samples are insufficient. This request and collection may take place at any point during the study, including during follow-up.

At baseline, if patient does not have frozen tissue available, fresh tissue must be obtained by biopsy. Biopsy of tumor will be repeated at or after progression (clinical or radiological) whether patient continues treatment post progression or not. If possible, biopsies at progression should be performed within 7 business days of documented disease progression, and optimally within 4 hours of taking that day's study medication. Please note that drug may be extended post progression (see section 4.1), and there is no need to hold drug for any length of time prior to the biopsy. In fact, patients will be requested to remain on study medication until the biopsy at progression is performed. If the treating physician decides to continue treatment at progression because the patient exhibits continued clinical benefit from therapy, the biopsy may be delayed until the investigator deems the biopsy feasible as long as patient safety is not compromised. Post-treatment biopsies will not be required for patients removed for reasons other than disease progression. See laboratory manual.

Note: For subjects who are withdrawn from study treatment, but are later placed back on the trametinib/dabrafenib combination therapy, a biopsy may be collected from the former study subject at the time of progression from the standard of care trametinib/dabrafenib therapy. These subjects must be re-consented and placed back on study to allow for attainment of a biopsy at progression.

Biopsies may be obtained by punch biopsy, core biopsy, or surgical excision, and may be performed by clinical personnel trained to do biopsies for standard of care collections. The number of - passes made through tumor per biopsy will be determined by the treating physician and the physician performing the biopsy procedure with primary consideration being safety. The tissue collected will be divided into aliquots (depending on size of collection, up to 4 aliquots per collection). For patients who co-enroll into LCCC1108 for NextGen sequencing, enough tissue will be collected for both kinomining and NextGen sequencing by

coordinating with the Study Coordinator of LCCC1108. When insufficient tissue samples are available to achieve both kinomining and NextGen sequencing, priority will be given to kinomining. Additional details regarding processing, storing and handling tissue will be provided in a separate laboratory manual.

Biological samples collected for the study will be stored at the research laboratories at the Lineberger Comprehensive Cancer Center (LCCC), University of North Carolina at Chapel Hill, NC until the completion of the study. With patient consent, any remaining tumor tissue after protocol specific studies are complete will be stored for future research concerning melanoma.

6.7.1 Biopsy Risks

The risks of these procedures are associated with a small risk of pain, bleeding, infection, and damage to adjacent organs. The magnitude of this risk depends somewhat upon the site of the procedure.

Potential risks according to site are:

Skin/chest wall (punch biopsy or surgical excision):

Likely: local discomfort and minor bleeding.

Less likely: moderate or major bleeding, or infection

Lymph node or soft tissue (punch biopsy or surgical excision):

Likely: local discomfort and minor bleeding.

Less likely: moderate or major bleeding, need for blood transfusion, hospitalization due to bleeding or other complications, infection, pneumothorax, damage to adjacent organs. Additional risks may be present if intravenous conscious sedation (IVCS) is required (see below).

Liver (core needle biopsy):

Likely: local discomfort and minor bleeding

Less likely: moderate or major bleeding, need for blood transfusion, hospitalization due to bleeding or other complications, infection, bowel perforation or damage to adjacent organs

Additional risks may be present if IVCS is required (see below).

Breast (core biopsy): punch biopsy or surgical excision

Likely: local discomfort and minor bleeding.

Less likely: moderate or major bleeding, need for blood transfusion, hospitalization due to bleeding or other complications, infection, pneumothorax, damage to adjacent organs.

In order to minimize the risk of a biopsy, only qualified personnel will perform these procedures. Prior to the procedure, the physician performing the procedure will discuss the risks with each study participant, answer any questions, and obtain a separate procedure consent. For biopsies of lesions that are not superficial and clearly palpable, imaging studies such as CT or ultrasound will be

used to guide the biopsy in order to minimize the risk of damage to adjacent structures. Patients receiving therapeutic anticoagulation, and patients with abnormal coagulation studies, neutropenia, or thrombocytopenia will not undergo biopsy until and unless these resolve because of the increased risk of potential complications under these circumstances. After lymph node biopsies, patients will be observed for approximately 2 hours (range 2-4 hours) after the procedure, or per institutional standard guidelines. After liver biopsies, patients will be observed for approximately 4 hours (range 4-6 hours) after the procedure, or per institutional standard guidelines. Less than the goal quantity of tissue is acceptable for each type of biopsy, and will be left to the clinical judgment of the physician performing the procedure.

6.7.2 Risks of Anesthesia

Local Anesthesia

All biopsy procedures require local anesthesia using lidocaine or related compounds. There is a small risk of an allergic reaction associated with these drugs.

In order to minimize the risk of local anesthesia, only qualified personnel will perform the biopsy procedure. Patients will be queried if they have had previous allergic reactions to local anesthetics.

Intravenous Conscious Sedation (IVCS)

Certain biopsy procedures, such as lymph node or liver biopsies, may require IVCS. IVCS is a minimally depressed level of consciousness that retains the patient's ability to maintain a patent airway independently and continuously and respond appropriately to physical stimulation and verbal commands. The medications used to induce conscious sedation include the benzodiazepine midazolam and the opioid agonist fentanyl, as per standard of care. IVCS is performed once over a 30-60 minute period, and may require administration of multiple doses of each agent over this time-frame. Rarely, IVCS will last longer than 60 minutes.

Midazolam:

See <http://www.drugs.com/pro/midazolam-injection.html> for complete prescribing information on midazolam, including complete information on risks associated with its use.

The risks of midazolam include respiratory depression and respiratory arrest, especially when used for sedation in non-critical settings. Respiratory arrest could require intubation. In very rare cases, when this was not recognized promptly and treated effectively, death or hypoxic encephalopathy has resulted. Other serious cardiorespiratory adverse events have occurred after administration of midazolam, including airway obstruction, oxygen desaturation, apnea, and cardiac arrest, rarely resulting in death or permanent neurologic injury. There have also been rare reports of hypotensive episodes requiring treatment,

particularly in patients with hemodynamic instability. Agitation, involuntary movements, hyperactivity and combativeness have been reported in adults patients treated with midazolam.

Concomitant use of midazolam with other respiratory depressants like fentanyl may increase the risk of hypoventilation, airway obstruction, desaturation or apnea, and may contribute to profound and/or prolonged drug effect. Prolonged sedation may also be seen midazolam is administered concomitantly with drugs known to inhibit the P450 3A4 enzyme system such as cimetidine, erythromycin, diltiazem, verapamil, ketoconazole and itraconazole.

Adverse effects reported after intravenous administration of a single dose when used as a sedative include the following (percentage is percentage of adult patients with adverse events): hiccoughs (3.9%), nausea (2.8%), vomiting (2.6%), coughing (1.3%), “oversedation” (1.6%), headache (1.5%), and drowsiness (1.2%). In addition, the following local effects at the site of the injection have been reported: tenderness (5.6%), pain during injection (5.0%), redness (2.6%), induration (1.7%), and phlebitis (0.4%). Additional rare (<1.0%) adverse events occurring when midazolam is used as a sedative include:

Respiratory (laryngospasm, bronchospasm, dyspnea, hyperventilation, wheezing, shallow respirations, airway obstruction, tachypnea);

Cardiovascular (bigeminy, premature ventricular contractions, vasovagal episode, bradycardia, tachycardia, nodal rhythm);

Gastrointestinal (acid taste, excessive salivation, retching);

CNS/Neuromuscular (retrograde amnesia, euphoria, hallucination, confusion, argumentativeness, nervousness, anxiety, grogginess, restlessness, emergence delirium or agitation, prolonged emergence from anesthesia, dreaming during emergence, sleep disturbance, insomnia, nightmares, athetoid movements, seizure-like activity, ataxia, dizziness, dysphoria, slurred speech, dysphonia, paresthesia);

Special Senses (blurred vision, diplopia, nystagmus, pinpoint pupils, cyclic movements of eyelids, visual disturbance, difficulty focusing eyes, ears blocked, loss of balance, light-headedness);

Integumentary (hive-like elevation at injection site, swelling or feeling of burning, warmth or coldness at injection site);

Hypersensitivity (allergic reactions including anaphylactoid reactions, hives, rash, pruritus);

Miscellaneous (yawning, lethargy, chills, weakness, toothache, faint feeling, hematoma)

Fentanyl

See <http://www.drugs.com/pro/fentanyl-injection.html> for complete prescribing information on fentanyl (Duragesic®), including complete information on risks associated with its use.

Fentanyl may cause muscle rigidity, particularly involving the muscles of respiration. Skeletal muscle movements in the extremities, neck and external eye have also been reported with fentanyl; rarely, these have been strong enough to pose patient management problems. Fentanyl may also produce euphoria, miosis, bradycardia and bronchoconstriction, as seen with other narcotic analgesics. The most common serious adverse reactions reported with fentanyl include respiratory depression, apnea, rigidity, and bradycardia. If these remain untreated, respiratory arrest, circulatory depression or cardiac arrest could occur. Other adverse reactions that have been reported are hypertension, hypotension, dizziness, blurred vision, nausea, emesis, laryngospasm and diaphoresis.

The risks of IVCS also include inhibition of the gag reflex and concomitant risk of aspiration and allergic reactions to the sedative or analgesic medications. The chances of serious risks from IVCS are small but real; for example, in a prospective study of 14,149 patients undergoing IVCS during upper gastrointestinal endoscopies, the rate of immediate cardiopulmonary events was 2 in 1000. The 30-day mortality was 1 per 2,000 cases. In this study, there was a strong association between lack of monitoring and use of high-dose benzodiazepines with adverse outcomes. There was also an association between the use of local anesthetic sprays to the oropharynx and the development of pneumonia.

In order to minimize the risk of IVCS, only qualified personnel (M.D. and R.N) will be responsible for conscious sedation. A minimum of two individuals will be involved in the care of patients undergoing conscious sedation—the physician performing the biopsy procedure, and the individual (R.N.) who monitors the patients and his/her response to both the sedation and the procedure, and who is capable of assisting with any supportive or resuscitative measures. The room where the procedure utilizing IVCS takes place in the interventional radiology suite will have adequate equipment to provide supplemental oxygen, monitor vital signs, and maintain an airway should this be necessary. An emergency cart will also be immediately accessible to the room where the procedure is to take place, and emergency support services will be available on page. Patients will be screened and evaluated for their fitness to undergo conscious sedation by a trained physician. Patients with active cardiac disease are excluded from this study. No local anesthetic spray to the oropharynx will be necessary, given that endoscopy is not a planned procedure. Following the procedure, patients will be observed closely in the recovery room according to standard institutional guidelines.

Risks of Imaging Studies

Some biopsy procedures require imaging studies, either to plan or guide the procedure. Imaging studies that may be used in obtaining tissue samples include CT scans and ultrasound. CT scans will expose study participants to controlled amounts of radiation. The total dose of radiation from these tests is not anticipated to cause any adverse effects. There is also a risk of an allergic reaction to the intravenous contrast dye used during CT imaging, as well as a risk

of experiencing feelings of anxiety or claustrophobia while undergoing a CT scan. There are no anticipated risks with the use of ultrasound.

In order to minimize these risks, patients will be queried, as per standard institutional practice, regarding their history of reactions to intravenous contrast dye. If a patient has had such a reaction, she/he will be premedicated, or dye will not be used, as per standard institutional practice. If a patient has previously experienced anxiety or claustrophobia while undergoing a CT scan, she/he will be encouraged to discuss this with her primary oncologist. Anxiolytics may be considered by the patient's primary oncologist as indicated.

